during these testing procedures, rest breaks will be provided to the subjects as needed and as requested by the subject. Please see the adjoining flowchart for a summary of the procedures that subjects in each study cohort will undergo. Subjects will not be randomized to the 2 cohorts. Assignment to the cohorts will be based on the lab/personnel and subject schedules. A subject can participate in the 2 cohorts sequentially. Also, participants in Cohort 2, when testing hypotheses comprising a repeated-measures comparison of different gait training strategies (e.g. Hypothesis 4a evaluating effect of walking speed; Hypothesis 4b comparing FastFES versus Fast), participants may cross-over between strategies within or across gait sessions.

1) Medical Clearance:

If a subject shows interest in participation in cohort 2 of the study (18 training sessions), before participation, we will obtain written medical clearance from the subject's physician (See attached Medical Clearance form). In addition, the subject will undergo clinical assessment to confirm that they are eligible for study participation.

2) Procedures for Clinical Assessment of Walking Function and Muscle Strength:

All subjects will review and sign consent forms before clinical testing. Clinical Testing will be performed by a licensed physical therapist. Clinical testing may comprise: (1) measurement of subjects' over ground self-selected (SS) walking speed (6-meter walk test); (2) over ground walking endurance measured by the distance ambulated during the 6-minute walk test; (3) assessment of gait and dynamic balance (measured using the functional gait assessment, 4-square step test, and the Berg balance score); (4) lower extremity portion of the Fugl-Meyer score⁷⁰; (5) step activity monitoring; (6) lower extremity proprioception (in which each limb segment will be flexed or extended approximately 10 degrees and the subject will be asked to identify whether the limb is moving and in what

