Burst superimposition during muscle strength testing: A technique called the burst superimposition technique will be used for measurement of the subject's muscle strength. This technique has been used to safely obtain a quick and accurate measurement of muscle strength in young and elderly able-bodied individuals as well as patient populations⁷¹⁻⁷³. For this technique, while the subjects are generating their maximal contraction force volitionally, a supra-maximal burst of electrical stimulation (100-Hz frequency, 100-ms duration, 600 μ s pulse duration) will be delivered to the muscle. The force generated by the muscles will be recorded via a force dynamometer. The 'true' force generating ability of the muscle will be calculated as the total force generated by the subject's volitional contraction and the superimposed electrical stimulation. The maximal contraction will be repeated 2 times for each leg.

3) **Cardiac Exercise Stress Test:**

After confirming the subject's eligibility for participation in the study and clinical testing, if the subject is part of Cohort 1 that will participate in the intensive 18-sessions of gait training, the subject will be referred for a cardiac exercise stress test (treadmill exercise test). The exercise stress test will be conducted under the supervision of a cardiologist at Emory University (referral will be provided as part of this research protocol). The stress test will help confirm that the subjects who participate in the intensive gait training

treatment sessions have sufficient cardiovascular health to participate in a treadmill exercise intervention. If a participant is unable to complete the stress test due to musculoskeletal impairments or other factors unrelated to cardiac health (e.g. muscle weakness, ankle instability, inability to walk at sufficiently fast speed or incline due to post-stroke muscle weakness), then the tolerance and appropriate dosage for treadmill training will be determined based on consultation with the cardiologist, exercise physiologist, and physical therapists.

4) Procedures for Gait Training Sessions:

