Note that data from Cohort 1 (case series on FastFES gait training) as well as data that evaluate Hypothesis 4b (i.e. a repeated-measures comparison of the short-term effects of FastFES versus Fast on corticospinal excitability and gait biomechanics) will inform the methodology, planning, and sample-size estimation for a future larger clinical trial.

At the beginning and end of each training session, a “**pre-test**” and “**post-test**” may be performed. The pre- and post-tests will comprise 30-second trials of treadmill walking at the subject's comfortable or fast walking speed. By obtaining data while

training at a standardized walking speed and while training without FES, we will be able to measure differences in motor learning among these training strategies. The procedures for motion analyses to be used for pre- and post-tests are described in a separate section (Procedures for Motion Analyses). In addition, for a few sessions, in addition to the 30-second walking trials, the pre- and post-test may comprise assessment of spinal or corticospinal excitability.

During the training sessions, subjects may wear a harness suspended from the ceiling (no body-weight support) for safety. In addition, if needed, the subjects will be allowed to hold on to the hand rails during walking. For stroke survivors, heart rate will be monitored throughout the session with a heart rate sensor that is placed on the chest under clothing (Polar USA, Lake Success, NY). If heart rate exceeds 80% of their age predicted heart rate maximum, walking will be stopped until it returns to baseline. In addition, blood pressure will be monitored at each rest break. If a subject's blood pressure exceeds 190/100 mmHg, the session will be stopped and their blood pressure will be continually monitored until it returns to baseline. Subjects will rate their perceived exertion on the Borg Scale of Perceived Exertion every 6 minutes. If a subject reaches level 13 on the Borg scale (i.e. between 'Fairly Light' and 'Somewhat hard') they will be given a rest break⁷⁴.

5) Procedures for Motion Analysis:

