
Procedures for MRI Scans (for a subset of 15 able-bodied individuals):

As stated above, the MRI scans will be obtained as part of a different IRB protocol. The IRB

protocols that we are requesting permission to use the brain MRI scans from are two protocols whose PI ([name]) is a co-investigator in the current IRB protocol: IRB00081268 (Noninvasive brain stimulation to evaluate neural plasticity after stroke) and IRB00072542 (Using concurrent brain imaging and stimulation to characterize brain behavior in stroke). The methods for the MRI will be as described in the above protocols, and for convenience are also listed here.

MRI acquisition: Scanning will be conducted at Emory University at the Center for Systems Imaging on a Siemens 3T Trio whole-body MRI scanner. A high-resolution T₁ scan (TR = 7.4ms, TE = 3.7ms, flip angle θ = 6°, FOV = 256mm, 160 slices, 1 mm thickness, scan time=3.2min) will be performed without contrast. The study team will have direct and immediate access to the data using Emory University's secure network server.

Risks

Risks associated with clinical testing, gait training, and motion analyses include falling, fatigue, poor heart rate and blood pressure response to walking and minor skin irritation from the adhesive tape. To minimize risk, subjects will wear a safety harness during the treadmill testing and will be given a rest break whenever requested. Heart rate will be monitored continuously and blood pressure will be monitored at rest breaks. If heart rate exceeds 80% of their age predicted heart rate maximum, walking will be stopped until it returns to baseline. If a subject's blood pressure exceeds 190/100 mmHg, the session will be stopped and their blood pressure will be continually monitored until it returns to baseline. The subject's primary or referring physician will be notified. Throughout the experiment, the experimenter has access to an emergency safety switch that can be used to stop the treadmill immediately. To ensure sufficient cardiovascular health to complete an intensive gait training program, stroke subjects who participate in 18 sessions of gait training (Cohort 1) will complete a cardiac exercise stress test.

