Subjects will not be anonymous to the researchers. As a first step during data management, subject identities will be de-identified by assigning each subject a number. Any computer files containing information that link the identifiable subject data with the de-identified subject number will be password protected and stored on a secure Emory University computer. Only de-identified data will be used to compile spreadsheets of the various outcome measures collected as part of this study (joint angles, clinical impairment scores, EMG, etc.). De-identified data may be stored for future use until 5-years after completion of the study. All signed consent forms will be stored in the subject's folder (organized by de-identified subject numbers) in a locked file cabinet at the University. Participants will not be audiotaped, photographed or videotaped without their permission during this study.

6. Participant selection

We plan to collect data on a sample of 55 individuals post-stroke and 35 able-bodied individuals. However, we anticipate a withdrawal rate of ~10%. Therefore, we will recruit 60 subjects and 45 able-bodied subjects.

Inclusion Criteria for Post-Stroke Subjects are: 1) age 30-80 years, 2) chronic stroke (>6 months post stroke), 3) first (single) lesion, 4) ambulatory with or without the use of a cane or walker, 5) sufficient cardiovascular health and ankle stability to walk for 6 minutes at their self-selected speed without an orthoses, 6) resting heart rate 40-100 beats per minute, 7) resting blood pressure between 90/60-70/90.

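### The resting blood pressure criterion for stroke participants prints an impossible systolic ceiling (70), so the plan states no usable upper systolic limit at entry

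*Combined protocol and SAP*

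**What the plan says.** Section 6 (Participant selection) lists seven inclusion criteria for stroke participants. The seventh is "resting blood pressure between 90/60-70/90". The criterion just before it, "resting heart rate 40-100 beats per minute", is an ordinary low-to-high range. The same section plans 60 stroke recruits for a sample of 55.

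Other parts of the document bear on cardiovascular fitness:

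- Inclusion criterion 5 asks for "sufficient cardiovascular health and ankle stability to walk for 6 minutes" at the participant's own pace. It gives no blood pressure figure.
- Section 5, item 1 (Medical Clearance) states, for people interested in cohort 2, that "before participation, we will obtain written medical clearance from" their physician. No threshold is attached.
- Section 5, item 3 (Cardiac Exercise Stress Test) sends Cohort 1 participants for a supervised treadmill test. It sets no resting limit.
- Section 5, item 4 (Procedures for Gait Training Sessions) says: "If a subject's blood pressure exceeds 190/100 mmHg, the session will be stopped". The same rule is repeated under Risks.

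**The concern.** An entry range for blood pressure needs a lower and an upper value for each of its two components, with the upper above the lower and systolic above diastolic in each pair. The upper pair printed here fails both conditions on the systolic side.

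This is an operative eligibility threshold. Taken literally, no stroke participant can qualify. In practice the staff who screen must be using a ceiling that the protocol does not state. Assessors could then apply different limits, and a monitor could not tell from the protocol whether an enrolled participant with a high resting systolic pressure was eligible. The participants have had a stroke, and many will do fast treadmill walking, so the upper systolic limit is the part of the criterion with the clearest safety purpose.

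**Working it through.** **Inputs.** Lower pair 90/60 and upper pair 70/90 (Section 6, stroke inclusion criterion 7); session stop 190/100 mmHg (Section 5, item 4, and Risks). Each pair is read as systolic/diastolic.

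**1. Systolic range as printed.** Ceiling minus floor = 70 − 90 = −20 mmHg. The interval is empty: no value is both at least 90 and at most 70.

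**2. Upper pair on its own.** Systolic minus diastolic = 70 − 90 = −20 mmHg. Systolic below diastolic is not physiologically possible.

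**3. Diastolic range as printed.** 90 − 60 = 30 mmHg, a valid interval. Its ceiling lies 100 − 90 = 10 mmHg below the diastolic stop, so the two are consistent.

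**4. Could the upper pair be transposed?** Read as 90/70, systolic would run from 90 to 90 and diastolic from 60 to 70. Only a systolic pressure of exactly 90 would be admitted, which is not a credible intention.

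**5. Could a leading digit be missing?** Restoring a digit *d* gives 100*d* + 70.

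| *d* | Ceiling (mmHg) | Against the 190 stop |
|---|---|---|
| 1 | 170 | 20 below |
| 2 to 9 | 270 to 970 | above |

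So 170 is the only repair of this kind that fits the session stop. It remains an assumption, since a different kind of slip would allow other values.

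**6. Is the limit given elsewhere?** The stroke exclusion criteria in Section 6 contain no blood pressure figure. Medical clearance, the stress test and criterion 5 carry no resting threshold. The only other blood pressure numbers are 190/100, which apply once a session is under way.

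**7. How uncertain is the intended ceiling?** Any whole number from 91 to 189 mmHg would lie above the printed floor and below the stop. As assumed examples, 140 would leave 190 − 140 = 50 mmHg before the stop, 170 would leave 20, and 180 would leave 10.

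**Result.** One of the four printed limits is unusable, three are usable, and the document does not allow the fourth to be recovered with certainty.

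**The case against.** The strongest counter-argument is that the fault may not be in the protocol. A digit could have been lost when the PDF was converted to text. Under Post-Stroke Gait Dysfunctions in Section 3, a word appears to be missing straight after a hyphen, which is where a lost 1 would sit here. Against that, the heart rate range in the adjacent criterion kept its 1 straight after a hyphen, and the criterion is running text rather than a table. The possibility stands, and it is why the source page should be checked first.

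A second argument is that the practical gap is small. The diastolic ceiling of 90 still excludes anyone whose hypertension includes a raised diastolic pressure, which leaves mainly isolated systolic elevation. Besides the safeguards already listed, there is an exclusion for medical conditions that limit walking, a rest break at Borg level 13, therapist guarding during Cohort 1 over ground walking, and blood pressure monitoring in the motion analysis sessions. Not every stroke participant trains fast: Cohort 2 may walk slowly, and the pilot experiments have no intervention. All of this is fair and lowers the safety consequence. None of it states a resting systolic figure. The stress test is limited to Cohort 1, and participants who cannot complete it for non-cardiac reasons may still train after consultation.

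It can also be said that this is a typographical slip that any reader would correct to 170. That is likely, but other ceilings would be equally coherent, and an eligibility limit should not depend on inference.

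**Conclusion.** The point holds. As the text reads, criterion 7 gives no usable upper systolic limit for stroke entry, and nothing else in the document supplies one. The fault is confined to one of four limits. It applies to all 60 planned stroke recruits and does not touch the hypotheses, the analysis or the power calculation. No conflict with the 190/100 stop is claimed, and nothing in the document shows that anyone was wrongly enrolled.

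The conclusion assumes that the pairs are systolic/diastolic and that the converted text matches the source page. If the source shows a valid ceiling such as 170/90, the point closes. Otherwise the criterion should be corrected, because it is a working safety threshold.

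**What to change.** 1. Check the source page for a lost digit.
2. If the text is as read here, amend criterion 7 to give two separate ranges in mmHg: systolic from 90 to the intended ceiling, and diastolic from 60 to 90. The clinical team should supply the ceiling and set it below the 190 mmHg session stop. The figure of 170 should not be adopted by default.
3. Check the recorded resting systolic pressures of stroke participants already enrolled against the ceiling that was intended when they were screened. A newly chosen limit should not be used to judge past enrolment.

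The cost is a one-line amendment and one review of existing screening records. The sample size and analysis do not change.

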The overall purpose of this protocol is to assess the biomechanical and neurophysiologic effects of rehabilitative strategies and protocols that are commonly used during physical therapy treatment of gait disorders post-stroke. As part of this protocol, 45 able-bodied individuals and 55 individuals with chronic stroke will be assigned to either Cohort 1 or Cohort 2, and will participate in 1-18 gait training sessions. If interested, study participants can also complete both study cohorts sequentially (with at least 3-weeks duration between switching from one cohort to the second). Evaluations for obtaining outcome measures will comprise clinical testing, muscle evaluations, gait analysis, and assessment of spinal and corticospinal excitability. Within Cohort 1 (stroke and able-bodied), 25 subjects will receive identical treatment throughout the training sessions (i.e. FastFES training). Within Cohort 2, 25 subjects will receive different rehabilitation strategies individually or in combination during each training session (e.g., treadmill walking, functional electrical stimulation, bio-feedback or verbal feedback about targeted walking parameters, split-belt walking, etc.). During gait training, Cohort 1 subjects will typically participate in a minimum of 2 and a maximum of 3 sessions per week. Subjects in Cohort 2 can participate in 1 to 18 gait training sessions but the frequency of the gait sessions can be varied according to the subject's and laboratory schedule (i.e. variable durations between consecutive sessions).

Aims

The aims of this protocol are to:

- 1) Study the changes in gait biomechanics, corticospinal excitability, and walking function during 18 sessions of gait retraining (Cohort 1).
- 2) Systematically determine the effect of parameters such as walking speed (slow, fast, variable, split-belt walking), functional electrical stimulation parameters (short-term changes induced by fast versus FastFES, stimulation intensity, number of muscles stimulated), and bio-

[figure not shown]
feedback on within-session changes in gait biomechanics, walking function, and corticospinal excitability (Cohort 2).

Hypotheses of the study

- By utilizing data collected on cohort 1 of subjects who undergo 18 sessions of FastFES gait retraining, the following hypothesis will be tested:

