Exclusion Criteria for Post-Stroke Subjects are: 1) evidence of moderate/ severe chronic white matter disease or cerebellar stroke on MRI, 2) cerebellar signs (ataxic ("drunken") gait or decreased coordination during rapid alternating hand or foot movements, 3) insulin dependent diabetes, 4) history of lower extremity joint replacement, 5) score of >1 on question 1b and >0 on question 1c on NIH Stroke Scale, 6) inability to communicate with investigators, 7) neglect/hemianopia, or unexplained dizziness in last 6 months, 8) neurologic conditions other than stroke, 9) orthopedic problems in the lower limbs or spine (or other medical conditions) that limit walking. Additional exclusion criteria for TMS (measurement of corticospinal excitability) are: 10) history of seizures, 11) metal implants in the head or face, 12) history of recurring or severe headaches/migraine, 13) headache within the past 24 hours, 14) presence of skull abnormalities or fractures, 15) hemorrhagic stroke, 16) history of dizziness, syncope, nausea, or loss of consciousness in the past 12 months.

Inclusion Criteria for Able-Bodied Individuals are: 1) age 21 to 80 years, 2) no history of neurologic disease, 3) no history of orthopedic disease or injury affecting the lower extremity.

Exclusion Criteria for Able-Bodied Individuals are: 1) history of neurologic disease, 2) history of orthopedic disease or injury to the lower extremity, 3) an implanted cardiac pacemaker. Additional exclusion criteria for the TMS portion of the study (corticospinal excitability measurement) are: 4) history of seizures, 5) metal implants in the head or face, 6) history of recurring or severe headaches/migraine, 7) headache within the past 24 hours, 8) presence of skull abnormalities or fractures.

Subject Recruitment. Study participants will be recruited from the general community within and outside Emory University.

Withdrawal from study. Participation in the present study will be voluntary and subjects will be able to opt out of the study at any time.

Our subject population will be representative of adult patients with stroke and healthy adults. The incidence of stroke is considered rare in children, estimated to be less than 13 cases per 100,000 children⁸⁸ and their inclusion would not provide additional information compared with the data gathered in adults.

7. Statistical analysis

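### Section 6 excludes able-bodied volunteers with a cardiac pacemaker, but no stroke criterion names one and the visible text gives no reason

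*Combined protocol and SAP*

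**What the plan says.** Section 6 (Participant selection) gives separate criteria for the two groups. For able-bodied volunteers the third exclusion is "3) an implanted cardiac pacemaker". The extra exclusions for TMS begin at item 4, so the pacemaker rule applies to every able-bodied participant.

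The stroke exclusions run from 1 to 16, with items 10 to 16 applying to TMS only. Two of them mention an implant or prosthesis: "4) history of lower extremity joint replacement" and, for TMS only, "11) metal implants in the head or face". The last general item is "9) orthopedic problems in the lower limbs or spine (or other medical conditions) that limit walking". On the cardiac side, the stroke inclusion criteria ask for "sufficient cardiovascular health and ankle stability to walk for 6 minutes at their self-selected speed", "resting heart rate 40-100 beats per minute" and a resting blood pressure range.

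Section 4 (Objectives) names both groups as recipients of the Cohort 1 training: "Within Cohort 1 (stroke and able-bodied), 25 subjects will receive identical treatment throughout the training sessions (i.e. FastFES training".

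**The concern.** The protocol treats a pacemaker as disqualifying in one group and says nothing about it in the other, although the group left unmentioned is the one for which the stimulation training was designed. Staff who apply Section 6 line by line would turn away an able-bodied pacemaker carrier. They would have no listed ground for turning away a stroke participant with the same device. What is at stake is the clarity of a safety-related eligibility rule. The statistical plan is untouched: no hypothesis, endpoint, analysis or sample size depends on it.

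**Working it through.** No formula applies. The check is a count of the criteria and a comparison of sections.

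**1. The two lists in Section 6**

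| | Able-bodied | Stroke |
|---|---|---|
| Inclusion criteria | 3 | 7 |
| General exclusions | 3 (items 1–3) | 9 (items 1–9) |
| TMS-only exclusions | 5 (items 4–8) | 7 (items 10–16) |
| Pacemaker named | Yes, general item 3 | No |

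The stroke exclusions total 9 + 7 = 16. Neither these nor the 7 inclusion criteria name an implanted cardiac device. The word pacemaker occurs once in the whole document, in the able-bodied list.

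**2. Could another stroke item cover it?** Item 4 concerns joints and item 11 concerns the head and face. Item 9 reaches other medical conditions only if they limit walking, which a pacemaker need not do. A resting heart rate between 40 and 100 does not exclude a paced rhythm.

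**3. Are stroke participants stimulated?** Yes, according to Section 5.
- Cohort 1 trains with electrical stimulation in all 18 sessions; in Cohort 2 it is one of the listed options (item 4).
- Strength testing may include a burst of stimulation above the maximal level (item 2).
- Spinal excitability may be tested by peripheral nerve stimulation (item 7).
- TMS is used unless the participant opts out (item 8).

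Section 10 gives stimulator limits of up to 150 V and 1 to 100 Hz without distinguishing the groups.

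**4. Do other checks supply a device rule?**
- *Physician clearance* (Section 5, item 1): "If a subject shows interest in participation in cohort 2 of the study (18 training sessions), before participation, we will obtain written medical clearance". The text ties it to Cohort 2, although the fixed 18-session programme is Cohort 1, so its reach is unclear. The form is not visible.
- *Stress test* (Section 5, item 3 and Risks): Cohort 1 only. It addresses tolerance of treadmill exercise. A participant who cannot complete it for non-cardiac reasons may proceed after consultation.
- *Heart-rate monitoring of stroke survivors* (Section 5, item 4): a stopping rule during sessions, not an entry rule.
- *Pilot experiments* (Section 2): these have no intervention component but may use brain and nerve stimulation for measurement. Neither the clearance nor the stress test clearly covers stroke participants in them.

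**5. A sign that the lists may not have been reconciled.** The Risks text in Section 5 cites syncope and seizure during TMS in able-bodied people and says that subjects with recent syncope or dizziness will be excluded. In Section 6 that exclusion for the past 12 months appears only in the stroke list (item 16). This is suggestive, not proof.

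**The case against.** The strongest reply is that the lists were never meant to mirror each other. Able-bodied volunteers face no other cardiac criterion, so a one-line device exclusion may do the work there. Stroke participants have heart-rate, blood-pressure and cardiovascular-health criteria, a cardiologist-supervised stress test in Cohort 1, and heart-rate monitoring during training. That is a plausible design and it weakens the inference of an oversight, at least for Cohort 1. It does not close the gap, because none of these checks states a device rule and they do not clearly reach every stroke participant.

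MRI is a second possible reason. Existing brain scans are used for a subset of 15 able-bodied people and for no stroke participant. However, the scans come from other protocols, the exclusion covers all able-bodied volunteers, and nothing in the text links the two.

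Third, a reader might infer from Section 4 that the two groups receive matched stimulation, which would rule out differing exposure as an explanation. The sentence does not say that. Set against the next statement about Cohort 2, and with Section 5, item 4, it means that training stays the same from session to session. What stands is that both groups are named as FastFES recipients.

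Finally, the Medical Clearance form and the consent pages are not visible and may contain a pacemaker question. The point therefore concerns the eligibility list only.

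**Conclusion.** The point holds as an unexplained inconsistency in a safety-related criterion. Every able-bodied pacemaker carrier is excluded, no stroke criterion mentions the device, and no visible text says why. Section 6 followed as written could admit a stroke participant with a pacemaker to functional electrical stimulation, burst stimulation, nerve stimulation or TMS.

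Its reach is the stroke group as a whole: Section 6 plans to recruit 60 in order to have data on 55. (Section 2 gives a stroke sample of 35.) The documents give no prevalence, so the number of carriers is unknown and could be zero.

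A reader might go further and infer that carriers are entering unscreened, or that the plan exposes them to a demonstrated danger. The documents support neither. Screening may happen on forms that are not shown, and the only internal sign that the device matters is the sponsor's own rule for the other group. The conclusion rests on that rule and on the visible text being complete as to eligibility criteria.

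**What to change.** In Section 6, add the able-bodied pacemaker criterion to the general exclusions for post-stroke subjects as a new item 10, and renumber the TMS-only items from 10–16 to 11–17. It must sit in the general list, because electrical stimulation is also given to participants who opt out of TMS. If the difference between the groups is deliberate, state the reason beside the criterion instead.

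The cost is one line of text and possibly a very small reduction in the eligible stroke pool. If the clearance form already screens for pacemakers, the change only brings Section 6 into line with practice.
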